5.2 ASSESSMENT OF EFFICACY

Efficacy will be assessed by evaluating the percentage of subjects reporting at the 12-month follow-up:

- Normalization of total distal acid exposure time or at least 50% reduction in total distal acid exposure time compared to baseline
- $\geq 50\%$ reduction in total GERD-HRQL score compared to baseline (off PPIs)
- $\geq 50\%$ reduction in average daily PPI dosage compared to baseline

6.0 SELECTION AND WITHDRAWAL OF SUBJECTS

6.1 INCLUSION CRITERIA

Subjects included in the study must meet all the following criteria:

1. Age >22 years
2. Laparoscopic sleeve gastrectomy (LSG) for obesity ≥ 12 months prior to proposed device implantation date.
3. Subject is a surgical candidate, i.e. is able to undergo general anesthesia and laparoscopic surgery.
4. Documented typical symptoms of GERD for longer than 6 months (regurgitation or heartburn which is defined as a burning epigastric or substernal pain which responds to acid neutralization or suppression).
5. Subject requires daily proton pump inhibitor or other anti-reflux drug therapy.

6. Total distal ambulatory esophageal pH must meet the following criteria: pH <4 for $\geq 4.5\%$ of the time. Note: Subjects shall have discontinued any GERD medications for at least 7 days prior to testing, with the exception of antacids up to the morning of testing.
7. Subjects with symptomatic improvement on PPI therapy demonstrated by a GERD-HRQL score of ≤ 10 **on** PPI and ≥ 15 **off** PPI, or subjects with a >6 point improvement when comparing their **on** PPI and **off** PPI GERD-HRQL scores.
8. GERD symptoms, in absence of PPI therapy (minimum 7 days).
9. If the subject is of child bearing potential must have a negative pregnancy test within one week prior to implant and must agree to use effective means of birth control during the course of the study.
10. Subject is willing and able to cooperate with follow-up examinations
11. Subject has been informed of the study procedures and the treatment and has signed an informed consent form.

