11.6 STANDARD OF CARE

As part of screening/baseline, all patients will undergo the standard of care anti-reflux surgery work-up. The anti-reflux surgery work-up used for the study enrollment should be completed within the 1-year time period prior to signing of the study ICF. For purposes of the study, the questionnaires (GERD-HRQL,

Foregut Symptom Questionnaire, and RDQ) will be considered standard of care to facilitate pre-screening of patients. However, only questionnaires completed by a subject who has provided informed consent for the study will be accessible to the Sponsor.

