Appendix: Table Shells and List of Listings to be Generated

Table shells are provided below for all summaries to be generated for this study. These shells are a guide to the general layout of data to be presented. Minor modifications can be made to suit existing programs or macros that are available. Additionally, a list of all listings to be created is provided corresponding to the eCRFs that are used during this study. All fields collected will be listed.

Table 1
Subject Disposition
All Subjects

Characteristics	Total
Signed Informed Consent	xx
Full Analysis Set	xx
Consented Screen Failure	xx
Device not implanted	xx (xx.x%)
Completed the Study [1]	xx (xx.x%)
Withdrawal from the Study [1]	xx (xx.x%)
Reason for Withdrawal [2]	
Withdrawal of consent	xx (xx.x%)
Adverse Event	xx (xx.x%)
Death	xx (xx.x%)
Lost to Follow-up	xx (xx.x%)
Site or Study Termination	xx (xx.x%)
Other	xx (xx.x%)

[1] Percentages are based on the number of subjects who enrolled and implanted as the denominator.

[2] Percentages are based on the number of subjects who discontinued from the study as the denominator.

<Programming note: Only categories observed in the database need to be displayed for Reason for Withdrawal.>

Table 2
 Subject Demographics and Physical Examination
 Full Analysis Set

Characteristic	Total (N = ##)
Age at Consent (years)	
n	xx
Mean (SD)	xx.x (xx.x)
Median (Min, Max)	xx.x (xx, xx)
Gender, n (%)	
Male	xx (xx.x%)
Female	xx (xx.x%)
Ethnicity, n (%)	
Hispanic or Latino	xx (xx.x%)
Not Hispanic or Latino	xx (xx.x%)
Not Reported	xx (xx.x%)
Race, n (%)	
American Indian or Alaska Native	xx (xx.x%)
Asian	xx (xx.x%)
Black or African American	xx (xx.x%)
Native Hawaiian or Other Pacific Islander	xx (xx.x%)
White or Caucasian	xx (xx.x%)
Other	xx (xx.x%)
Height (cm)	
n	xx
Mean (SD)	xx.x (xx.x)
Median (Min, Max)	xx.x (xx, xx)
Weight (kg)	
n	xx
Mean (SD)	xx.x (xx.x)
Median (Min, Max)	xx.x (xx, xx)
Body Mass Index (kg/m ²) at Baseline	
n	xx
Mean (SD)	xx.x (xx.x)
Median (Min, Max)	xx.x (xx, xx)

Denominator and percentages are based on subjects with non-missing data.

<Programming note: Only categories observed in the database need to be displayed for Ethnicity and Race>

Table 3
GERD Medications
Full Analysis Set

Characteristic	Baseline (N = ##)	3 Months Follow-Up (N = ##)	6 Months Follow-Up (N = ##)	12 Months Follow-Up (N = ##)
Currently Taking PPI				
Yes	xx (xx.x%)	xx (xx.x%)	xx (xx.x%)	xx (xx.x%)
No	xx (xx.x%)	xx (xx.x%)	xx (xx.x%)	xx (xx.x%)
PPI Medications				

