Number of Subjects with at Least 50% Reduction on GERD-HRQL				xx (xx.x%)

Denominator and percentages are based on subjects completed baseline and 12 months follow-up per protocol requirements.

[1] % Successful is defined as number of subjects meeting the success criterion of at least 50% reduction on GERD-HRQL at 12 months follow-up compared to baseline off PPI.

Table 15
 Daily PPI Medication Use from Baseline to 12 Months
 Full Analysis Set

Parameter	Baseline	12 Months Follow-Up	Change from Baseline to 12 Months Follow-Up	% Successful at 12 Months Follow-Up [1]
PPI Use (mg) [2]				
n	xx	xx	xx	
Mean (SD)	xx.x (xx.x)	xx.x (xx.x)	xx.x (xx.x)	
Median (Min, Max)	xx.x (xx, xx)	xx.x (xx, xx)	xx.x (xx, xx)	
95% Confidence Interval			(xx.xxx, xx.xxx)	
Number of Subjects with at Least 50% Reduction in Daily Use				xx (xx.x%)

Denominator and percentages are based on subjects completed baseline and 12 months follow-up.

[1] % Successful is defined as number of subjects meeting the success criterion of at least 50% reduction in daily PPI use from baseline at 12 months.

[2] PPI Use is defined by the evaluation of subject's daily dose of PPI.

<Programming note those PPI administrated as PRN will not be included in daily dose calculation..>

Table 16
 Abdominal/Chest X-Ray at 12 Months Follow-Up
 Full Analysis Set

Characteristic	12 Months Follow-Up (N = ##)
Is the LINX device at the gastroesophageal junction?	
Yes	xx.x (xx.x)
No	xx.x (xx.x)
Any Evidence of Device Migration?	
Yes	xx (xx.x%)
No	xx (xx.x%)

Denominator and percentages are based on subjects with non-missing data.

Table 17
 Foregut Symptoms Questionnaire by Visit (Off PPI)
 Full Analysis Set

Characteristic	Baseline (N = ##)	3 Months Follow-Up (N = ##)	6 Months Follow-Up (N = ##)	12 Months Follow-Up (N = ##)
Regurgitation Frequency				
None	xx (xx.x%)	xx (xx.x%)	xx (xx.x%)	xx (xx.x%)
Mild	xx (xx.x%)	xx (xx.x%)	xx (xx.x%)	xx (xx.x%)
Moderate	xx (xx.x%)	xx (xx.x%)	xx (xx.x%)	xx (xx.x%)
Severe	xx (xx.x%)	xx (xx.x%)	xx (xx.x%)	xx (xx.x%)
Lung Problems				
None	xx (xx.x%)	xx (xx.x%)	xx (xx.x%)	xx (xx.x%)
Recurrent cough	xx (xx.x%)	xx (xx.x%)	xx (xx.x%)	xx (xx.x%)
Nocturnal cough	xx (xx.x%)	xx (xx.x%)	xx (xx.x%)	xx (xx.x%)
Recurrent pneumonitis	xx (xx.x%)	xx (xx.x%)	xx (xx.x%)	xx (xx.x%)
Asthma	xx (xx.x%)	xx (xx.x%)	xx (xx.x%)	xx (xx.x%)
Change of voice	xx (xx.x%)	xx (xx.x%)	xx (xx.x%)	xx (xx.x%)
Other	xx (xx.x%)	xx (xx.x%)	xx (xx.x%)	xx (xx.x%)
Ability to Vomit				

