< Programming note: Explants are identified from the Adverse Event case report form under the "EXPLANT" checked (variable name AEEXPLANT), or in the Subject Withdrawal/Study Completion case report form under the "Reason for Withdrawal/Completion is Investigator withdrawal" selected "Device explant" (variable name DSINVESWIT=1). Time to explant in months is calculated based on either the date of explant from the AE form and the date of original implant = (AEINTERDAT1 - IMPLANTSURGDAT)/30.4375; or the date of explant mentioned in detailed reason for withdrawal/completion = (explant date derived from DSREAS1 - IMPLANTSURGDAT)/30.4375. >

Table 29
Daily PPI Use
Full Analysis Set

Characteristic	3 Months Follow-Up (N = ##)	6 Months Follow-Up (N = ##)	12 Months Follow-Up (N = ##)
Discontinue Daily PPI Use			
Yes	xx (xx.x%)	xx (xx.x%)	xx (xx.x%)
No	xx (xx.x%)	xx (xx.x%)	xx (xx.x%)

Percentages are calculated using the total number of subjects completed the 3 months, 6 months, and 12 months follow-up.

<Programming note: Discontinue Daily PPI Use is defined as subjects who reported PPI medication usage at screening/baseline but no PPI usage in each follow-up visit. (GERDMEDPPI =Yes and MEDFUPPI =No)>

The following listings will be generated for this study:

Listing 1	Inclusion/Exclusion Criteria All Subjects
Listing 2	Demographics Full Analysis Set
Listing 3	Study Visit Assessment Full Analysis Set
Listing 4	Physical Examination Full Analysis Set
Listing 5	pH Results Full Analysis Set
Listing 6	Manometry/Motility Results Full Analysis Set
Listing 7	Endoscopy Data Full Analysis Set
Listing 8	Implantation Data Full Analysis Set
Listing 9	Barium Esophagram Data Full Analysis Set
Listing 10	GERD Medications Full Analysis Set
Listing 11	LSG and GERD History Full Analysis Set
Listing 12	Motivation for Surgery Full Analysis Set
Listing 13	GERD-HRQL Questionnaire (on PPI) Full Analysis Set
Listing 14	GERD-HRQL Questionnaire (off PPI) Full Analysis Set
Listing 15	Abdominal/Chest X-Rays Data Full Analysis Set

Listing 16	Discharge Full Analysis Set
Listing 17	Follow-Up GERD Medications Full Analysis Set
Listing 18	GERD-HRQL Questionnaire Full Analysis Set
Listing 19	Foregut Symptoms Questionnaire Full Analysis Set
Listing 20	Adverse Event Full Analysis Set
Listing 21	Protocol Deviations All Subjects
Listing 22	Subject Withdrawal/Study Completion All Subjects
Listing 23	Unscheduled Visit All Subjects

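### Neither PPI responder table restricts its denominator to baseline PPI users: non-users dilute the Table 29 rate, and a zero baseline dose leaves the Table 15 result to coding

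*Protocol*

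**What the plan says.** **Eligibility.** Protocol 6.1, criterion 5: "Subject requires daily proton pump inhibitor or other anti-reflux drug therapy". A PPI is one way to qualify, not the only one. Criterion 7 admits "Subjects with symptomatic improvement on PPI therapy demonstrated by a GERD-HRQL score of" at most 10 on PPI and at least 15 off it, or a difference of more than 6 points between the two. Every eligible subject has therefore taken a PPI at some time. No criterion requires a scheduled daily PPI at baseline. Protocol 11.6 adds that the surgical work-up "should be completed within the 1-year time period prior to signing of the study ICF".

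**Table 15 (SAP appendix), at least 50% reduction in daily PPI use.** The denominator footnote is "Denominator and percentages are based on subjects completed baseline and 12 months follow-up". The programming note says that "those PPI administrated as PRN will not be included in daily dose calculation". No rule is given for a baseline dose of zero.

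**Table 29 (SAP appendix), discontinuation of daily PPI use at 3, 6 and 12 months.** The footnote is "Percentages are calculated using the total number of subjects completed the 3 months, 6 months, and 12 months follow-up". The note defines success as "subjects who reported PPI medication usage at screening/baseline but no PPI usage in each follow-up visit", coded GERDMEDPPI=Yes with MEDFUPPI=No. It does not mention PRN use.

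**Table 18 (SAP appendix), elimination of regurgitation.** Here the percentages are limited to subjects who had the symptom at baseline and returned the questionnaire at that visit.

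**The concern.** A responder rate for reducing or stopping a drug describes only subjects who were taking it. Two different groups can enter these tables without a scheduled dose to reduce: subjects on another anti-reflux drug and no PPI, and subjects who take a PPI only as needed. The SAP excludes neither group from either denominator, and the two tables treat PRN use differently.

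PPI reduction is one of the three efficacy endpoints, the study is intended to support a labeling change, and at most 30 subjects are planned. A handful of such subjects could move the reported percentage noticeably, in a direction set by an unstated programming choice.

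**Working it through.** The documents give no PPI rate, so there is no figure to reproduce. The check is one of logic, followed by an illustration.

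**Table 29.** Let n be the subjects counted at a visit, k those with GERDMEDPPI=No, and s the successes among the other n−k. The numerator requires GERDMEDPPI=Yes, so the k subjects can never enter it.

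- As written: s/n. Among baseline users: s/(n−k). Ratio: (n−k)/n.
- At n=30 the ratio is 29/30=0.967 for k=1, 27/30=0.900 for k=3 and 24/30=0.800 for k=6.
- A PRN-only baseline user has reported PPI use, so GERDMEDPPI=Yes as the note is written. That subject succeeds if no PPI is reported at follow-up and causes no dilution.

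**Table 15.** Here k counts subjects with no scheduled baseline dose: non-users and, if leaving out PRN is read as 0 mg, PRN-only users. With baseline dose B=0 and 12-month dose F, the percent reduction (B−F)/B has a zero denominator. Three plausible codings of the same criterion disagree when F=0:

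- Percent change: 0/0, hence missing. The subject either drops out or, if kept in the footnoted denominator, counts as a failure.
- F ≤ 0.5×B, or B−F ≥ 0.5×B: 0 ≤ 0 or 0 ≥ 0, hence a success.
- F < 0.5×B: 0 < 0 is false, hence a failure.

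With F>0, for example 20 mg, none of the three comparisons is met.

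**Size for Table 15.** The values of n, k and the response among the other n−k (about 80%) are assumptions. The last column also assumes that every zero-baseline subject is at 0 mg at 12 months.

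| n | k | s | failure, s/n | excluded, s/(n−k) | success, (s+k)/n |
|---|---|---|---|---|---|
| 30 | 0 | 24 | 80.0% | 80.0% | 80.0% |
| 30 | 1 | 23 | 76.7% | 79.3% | 80.0% |
| 30 | 3 | 22 | 73.3% | 81.5% | 83.3% |
| 30 | 6 | 19 | 63.3% | 79.2% | 83.3% |
| 20 | 3 | 14 | 70.0% | 82.4% | 85.0% |

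The gap between the failure and success codings is k/n: 3.3, 10.0 and 20.0 points for k=1, 3 and 6 at n=30. For n=30 and k=3, exact Clopper-Pearson 95% intervals are 54.1–87.7% (22/30), 61.9–93.7% (22/27) and 65.3–94.4% (25/30). SAP 8.5.3 names no interval method for this endpoint. Clopper-Pearson is assumed here because SAP 8.5.1 names it for pH.

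**PRN across the two tables.** A subject who moves from a scheduled dose to PRN use by 12 months has no counted dose in Table 15. If that is read as 0 mg, the subject is a full responder there. In Table 29 the same subject still reports PPI use and is classed as not discontinued.

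**The case against.** The strongest reply is that the affected group may be empty. Criterion 7 needs a response shown on and off PPI, criterion 8 needs symptoms without PPI, Protocol Table 3 collects duration of PPI use at baseline, and SAP Table 12 is built on an on-PPI baseline score. The "Currently Taking PPI" row in SAP Table 3 is a generic Yes/No shell shared with the follow-up columns, so its No line does not show that baseline non-users were expected. This stands as to frequency. It does not close the route: PPI response within the past year is not a scheduled daily dose at baseline. The Table 29 numerator itself conditions on baseline use, while its denominator does not.

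Four stronger readings are tempting, and the documents do not support them:

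- *Zero-dose subjects cannot succeed in either table.* In Table 15 the outcome depends on coding, and a literal non-strict threshold makes 0 mg to 0 mg a success. In Table 29 PRN-only users can succeed.
- *Both rates are wrong.* That depends on k, which the documents do not give. The effect is nil at k=0.
- *The Table 29 denominator means completers of all three visits.* The footnote can be parsed that way, but each column has its own N, so a per-visit reading is the natural one.
- *A later start of scheduled PPI would be lost.* It would still appear in SAP Table 3 and Listing 17.

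It is also fair to say that the study is descriptive, with no hypothesis or success threshold, so no formal decision turns on the rate. It is nevertheless a reported efficacy endpoint and needs a defined result for every subject in its denominator. Finally, the PRN note does not literally say that the dose is set to zero. It could equally mean that no dose is calculable, in which case a PRN-only subject might drop out as unobserved. That is one more reason to state the rule.

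**Conclusion.** The point holds in a limited form. For Table 29 the defect follows from the stated definitions: any baseline non-user is counted as not discontinued, and the rate is diluted by (n−k)/n. For Table 15 the defect is a missing rule, not a bias of known direction. Under the assumed n=30, k=3 and 22 responders among 27, the same data give 73.3%, 81.5% or 83.3%. All sizes rest on assumed n, k and response, and k is probably small because of criterion 7. The change is worth making because the remedy is nearly free and Table 18 already applies the needed convention.

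**What to change.** - **Table 15:** limit the responder denominator to subjects with a scheduled daily PPI dose above zero at baseline and with 12-month data. Report zero-baseline subjects in a separate row with their 12-month dose.
- **Table 29:** at each visit, use baseline PPI users who have medication data at that visit, as Table 18 does for regurgitation.
- **PRN use:** state one treatment and apply it in both tables, at baseline and at follow-up. Say whether a PRN-only subject has a dose of zero or no calculable dose.

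The cost is two revised footnotes, a sentence on PRN use and a filter in the code. The downside is a slightly smaller denominator and, at a given rate, a somewhat wider confidence interval. Showing the number of excluded subjects lets a reader recover the unrestricted rate.

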6.2 EXCLUSION CRITERIA

Subjects should be excluded from the study based on the following criteria:

1. The procedure is an emergency procedure.
2. Suspected or known allergies to titanium, stainless steel, nickel, or ferrous materials.
3. Presence of >3 cm hiatal hernia as determined by endoscopy or barium esophagram.
4. Subject had any major complications related to the laparoscopic sleeve gastrectomy that may interfere with, or increase the risks of the LINX procedure (such as, but not limited to, leaks from the gastric remnant and infection at the sleeve gastrectomy)
5. Plans to surgically revise the gastric pouch (either known preoperatively or decided intraoperatively)
6. Currently being treated with another investigational drug or investigational device.
7. Suspected or confirmed esophageal or gastric cancer or prior gastric or esophageal surgery or endoscopic intervention for GERD (with the exception of sleeve gastrectomy).
8. Distal amplitude <35 mmHg or <70% peristaltic sequences (if using Conventional Manometry)

-or-

If using High Resolution Manometry (exclude for any of the following):

- Distal Contractile Integral (DCI) ≤ 450 mmHg·s·cm or
- $\geq 50\%$ ineffective swallows or
- $\geq 50\%$ fragmented swallows

(Fragmented swallows are defined as those with a ≥ 5 cm break [large] in peristaltic integrity)

9. Presence of esophagitis – Grade C or D (LA Classification).
10. BMI >35.
11. Symptoms of dysphagia more than once per week within the last 3 months.
12. Diagnosed with Scleroderma.
13. Diagnosed with an esophageal motility disorder such as but not limited to achalasia, nutcracker esophagus, or diffuse esophageal spasm or hypertensive LES.
14. Subject has a history of or known esophageal stricture or gross esophageal anatomic abnormalities (Schatzki's ring, obstructive lesions, etc.)
15. Subject has esophageal or gastric varices
16. History of/or known Barrett's esophagus.
*Note: The diagnosis of Barrett's esophagus requires both **endoscopic** and **histologic** evidence of metaplastic columnar epithelium. Endoscopically, there must be columnar epithelium within the esophagus. Histologically, the epithelium must be metaplastic, as defined by the presence of goblet cells.*
17. Subject cannot understand trial requirements or is unable to comply with follow-up schedule
18. Pregnant or nursing, or plans to become pregnant during the course of the study.
19. Any reason which the Investigator believes may cause the subject to be non-compliant with or unable to meet the protocol requirements.
20. Subject has an electrical implant or metallic, abdominal implants.

7.0 STUDY SCHEDULE AND ASSESSMENTS

Table 1 provides a schedule of data collection and follow-up windows. It should be noted that certain data is collected while on and/or off GERD medications.

Standard of care practices for antireflux surgery will be the basis of the assessments performed to determine if a subject is a candidate for the LINX device. Investigators should refer to the LINX Instructions for Use (IFU) for prescribing information (see **Appendix A**). Further, the study center will obtain appropriate study informed consent prior to evaluating the subject study specific evaluations. Data will then be collected at the screening/baseline visit, the implant procedure and the hospitalization period following implant until discharge. The subject will be followed at 2-weeks, 3-months, 6-months, and 12-months post-implant, with data collection occurring at each time point. Follow-up assessments may be completed by telephone or visit, with the exception of the X-rays, manometry, barium swallow, endoscopy and esophageal pH testing which must be conducted during a visit.

Subjects will complete questionnaires to evaluate reflux-related symptoms (GERD-HRQL and Foregut Symptom Questionnaire). With the exception of the GERD-HRQL

at baseline, the questionnaires are completed off GERD medications for at least 7 days, with the exception of antacids which can be taken up until the morning of assessment. At the screening/baseline visit, the questionnaires will be completed twice for the GERD-HRQL – once on GERD medications and once off GERD medications for at least 7 days, with the exception of antacids which can be taken up until the morning of assessment (Table 2).

Table 1: Schedule of Data Collection and Follow-Up Windows

Screening/ Baseline	Implant /Discharge	2-week Post-Operative Visit (Day 7 – Day 21)	3 months (Day 76 – Day 104)	6 months (Day 150 – Day 210)	12-month Visit (Day 305 – Day 425)	Data Collected
X						Demographics (gender, race)
X					X	Height and Weight
X					X	Medical History
	X					Implant Procedure and Discharge Data
X					X	Endoscopy (LA Grade Classification)
X					X	Manometry/Motility
X	X ³				X	Barium Esophagram
	X ³				X	Upright, Bi-Planar X-Rays (AP and Lateral)
X			X	X	X	GERD Medications
X ¹			X ²	X ²	X ²	GERD-HRQL
X ²			X ²	X ²	X ²	Foregut Symptom Questionnaire
X ²					X ²	Esophageal pH Measurements (off PPIs)
	X	X	X	X	X	Device and/or Procedure Adverse Events

X=All study subjects

¹Screening/baseline GERD-HRQL questionnaire is completed twice: once on GERD medication and once off GERD medications for at least 7 days, with the exception of antacids which can be taken up until the morning of assessment.

² Completed/conducted off GERD medications for at least 7 days, with the exception of antacids which can be taken up until the morning of assessment.

³Testing performed after implant and prior to discharge or within 7 days of implant, whichever occurs first.

Table 2: Completion of Questionnaires and GERD Medication

Visit	GERD-HRQL	Foregut
Baseline/Screening	On GERD medications Off GERD medications	Off GERD medications
3-Month	Off GERD medications	Off GERD medications
6-Month	Off GERD medications	Off GERD medications
12-Month	Off GERD medications	Off GERD medications

The data detailed in **Table 3** will be obtained at each of the identified time points. Use the following guidelines provide suggested methods and documentation for testing (**Appendix B**):

- 4663 Guidelines for Endoscopy testing
- 4664 Guidelines for X-rays testing
- 4665 Guidelines for Barium Esophagram testing
- 4666 Guidelines for Manometry/Motility testing

Table 3: Planned Assessments

Visit	Assessments/Data to be Collected
Screening/ Baseline	
 • Informed Consent • Demographics (Date of Birth, Gender, Race) • Height and weight • GERD History: Duration of PPI use, Years with GERD, GERD New Onset or Pre-existing after LSG • GERD-HRQL (on/off PPIs) and Foregut Symptoms Questionnaire (off PPIs) • Baseline GERD related medication use • Esophageal pH measurements (off PPIs) • Endoscopy • Manometry/Motility • Barium Esophagram • Motivation for surgery • Inclusion/Exclusion criteria evaluation
Implant/ Discharge	
 • Surgery Date • Surgery start and stop time • Implanted device size • Concomitant procedures (e.g. hiatal hernia repair, cholecystectomy) • Barium esophagram and upright Bi-Planar X-Rays (AP and Lateral) • Discharge Date • Perioperative and device and/or procedure related adverse events
2 Week	
 • Device and/or procedure related adverse events
3-Month	
 • GERD-related medication use within the last 30 days • GERD-HRQL (off PPIs) and Foregut Symptoms Questionnaire (off PPIs) • Device and/or procedure related adverse events
6-Month	
 • GERD-related medication use within the last 30 days • GERD-HRQL (off PPIs) and Foregut Symptoms Questionnaire (off PPIs) • Device and/or procedure related adverse events

[figure not shown]
Visit	Assessments/Data to be Collected
12 Month Follow-up	
 • Height and weight • GERD-HRQL (off PPIs) and Foregut Symptoms Questionnaire (off PPIs) • GERD-related medication use within the last 30 days • Esophageal pH testing (off PPIs) • Manometry/motility • Endoscopy • Barium esophagram and upright Bi-Planar X-Rays • Device and/or procedure related adverse events

The data collection window for each visit is outlined in **Table 4**. The 2-week follow-up visit is +/- 7 days from the anniversary of the implant procedure. The 3-month follow-up visit is +/- 14 days from the anniversary of the implant procedure. The 6-month follow-up visit is +/- 30 days from the anniversary date of the implant procedure. The 12-month follow-up visit is +/- 60 days from the anniversary date of the implant procedure.

Table 4: Follow-up Windows

Visit	Follow-up Window
2-week (+7 days)	7—21 days
3 months (+14 days)	76–104 days
6 months (+30 days)	150-210 days
12 Months (+60 days)	305-425 days

